6.5 IN-PERSON DIAGNOSTIC TESTING

N/A

6.6 COGNITIVE BATTERY TESTING

All children will complete cognitive assessments at the following time points:

- Baseline
- Month 6

The tests included are as follows:

Double Trouble - 1:30 timed test

 Based off of a classic Stroop test, Double Trouble measures selective attention, processing speed, and the brain's ability to focus on specific information when presented with conflicting and layered stimuli

Feature Match - 1:30 timed test

 Feature Match is a focus and processing task that requires surveying an increasingly difficult array of information and rapidly assessing the correct response while holding previously processed and detailed information in attention

Grammatical Reasoning - 1:30 timed test

Grammatical Reasoning is a deductive reasoning task that requires quickly interpreting
phrases and making logical conclusions from understanding. Variation between text and
shapes on screen require holding key information in short-term memory in order to
properly complete the task, leveraging the same parts of the brain that enable an
individual to remain focused between varied stimuli.

Digit Span - performance-based test (3-4 min)

Increasing in length after each successful attempt, Digit Span requires users to focus
on displayed numbers, hold them in short-term memory, and repeat them back correctly,
thereby showing cognitive flexibility and the brain's ability to perform memory and
attention related tasks without error

Token Search - performance-based test (3-4 min)

Leveraging the brain's executive functioning skills, Token Search requires participants
to hold information in working memory and remain focused on completing sequential
steps without making mistakes. The tasks become increasingly difficult, requiring more
active utilization of brain regions associated with processing, attention, and memory as
the task continues.

6.7 REQUIRED DEVICES

Participants require access to a computer, laptop, or tablet to complete the cognitive assessments.

All participants will be provided with the FitBit Smart Scale and the Ultrasonic Height Measuring Stadiometer required for the height and weight measurements.

7 STATISTICAL CONSIDERATIONS

Following data collection and the completion of the trial, the data will be analyzed by Citruslabs to determine the effect of the intervention versus the placebo. Between-arm and participant repeated measures between time point statistical tests will be used to examine differences in health outcomes during the study and compared to the placebo. Percentages of people who experienced improvements will also be examined. The analysis will adopt an intent-to-treat (ITT) approach, reflecting the primary objective of assessing the effectiveness of the test product as it would be used in the general population, inclusive of all randomized participants, irrespective of adherence or protocol deviations.

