1.3 SCHEDULE OF ACTIVITIES (SOA)

Procedures	Screening	Intervention	Conclusion
Informed Consent	х		
Demographics	х		
Inclusion/ Exclusion	х		
Administer Study Intervention		х	
Questionnaires	х	Х	х
Height & Weight Measurements	х	х	х
Cognitive Battery Testing	х		х
Adverse event Review and Evaluation	х	Х	Х

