2.2 RISK/BENEFIT ASSESSMENT

Immediate risks:

There are no predicted risks associated with this product. However, some people may experience adverse reactions when trying a new product. NuBest Tall Protein contains milk-based ingredients, so it is not suggested for those with a dairy allergy. It does not contain soy, grain, wheat, GMO, or gluten.

As dairy can interact with a number of medications, all medications should be separated by a minimum of 4 hours from taking the test product.

Long-term risks:

There are no predicted long-term risks related to using this product. Any short-term risk should dissipate after discontinuing the test product.

Immediate benefits:

Participants may experience positive changes in overall health. Also, participants might experience increased energy levels, immune function, and overall well-being.

Long-term benefits:

Participants may experience an increase in height, maintenance of a healthy weight, and enhanced quality of life due to an increase in overall health.

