3 OBJECTIVES AND ENDPOINTS

OBJECTIVES	ENDPOINTS	TIMEPOINTS	ASSESSED BY	JUSTIFICATION FOR ENDPOINTS
Primary				
To examine the effect of the NuBest Tall Growth Protein Powder cognitive function.	Improvement in score on assessments: • Double Trouble • Feature Match • Grammatical Reasoning • Digit Span • Token Search	Baseline and Month 6	Cognitive Battery Testing	The combination of these cognitive assessments will provide objective data on the efficacy of the product in improving specific domains of cognitive function.
Secondary				
	Increase in height			

	Maintenance of a healthy weight	Baseline, Month 2, Month 4, Month 6 (height & weight measurements)	Height measured using an Ultrasonic Height	
To investigate the impact of the NuBest Tall Growth Protein Powder on a range of health parameters, including height, weight, energy levels, immune function, and digestion.	Increase energy levels		Measuring Stadiometer	The combination of objective measurements and questionnaires will provide both independent and participant perception data on secondary health parameters.
	Improved signs of digestive health		Weight measured using a FitBit Smart Scale.	
	Increased immune	Baseline, Month 1, Month 2, Month 3, Month 4, Month 5, Month 6.		
	function (assessed via the number of times the child has been ill in the past 6 months)		Study-specific questionnaires	

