6.4 PARTICIPANT DISCONTINUATION/WITHDRAWAL FROM THE STUDY

Participants are free to withdraw from participation in the study at any time upon request.

An investigator may discontinue or withdraw a participant from the study for the following reasons:

- Pregnancy
- Significant study intervention non-compliance
- If any clinical adverse event (AE), laboratory abnormality, or other medical condition or situation occurs such that continued participation in the study would not be in the best interest of the participant
- Disease progression which requires discontinuation of the study intervention
- If the participant meets an exclusion criterion (either newly developed or not previously recognized) that precludes further study participation
- Participant should be withdrawn from the study if they start on a new drug or receive antibiotics

The reason for participant discontinuation or withdrawal from the study will be recorded on a Case Report Form (CRF). Participants who sign the informed consent form but do not receive the study intervention may be replaced. Participants who sign the informed consent form, receive the study intervention, and subsequently withdraw, or are withdrawn or discontinued from the study, will not be replaced.

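### Adverse events are reviewed in every phase but never summarised by arm, and the only categorical summary counts improvement, so discrete harms and worsening in a subset of children may go unreported.

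*Combined protocol and SAP*

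**What the plan says.** The schedule in Section 1.3 has a row for "Adverse event Review and Evaluation", ticked for screening, intervention and conclusion. Section 2.2 predicts no risks from the product but accepts that "some people may experience adverse reactions when trying a new product".

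The table in Section 3 has two objectives. The primary is "To examine the effect of the NuBest Tall Growth Protein Powder cognitive function". The secondary concerns effects "on a range of health parameters, including height, weight, energy levels, immune function, and digestion". Neither is a safety or tolerability objective. Digestion appears as the endpoint "Improved signs of digestive health", and Section 3 assigns it to study-specific questionnaires.

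Section 7 is the whole statistical plan. It states that "Between-arm and participant repeated measures between time point statistical tests will be used to examine differences in health outcomes during the study", with comparison against placebo, and then that "Percentages of people who experienced improvements will also be examined". It adopts intention-to-treat for all randomised participants. It does not mention adverse events, a safety population or the sidedness of any test.

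Section 6.4 contains the only stated use of an adverse event. "If any clinical adverse event (AE), laboratory abnormality, or other medical condition or situation occurs" opens one of the grounds on which the investigator may withdraw a participant, and the reason for withdrawal goes on a case report form.

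**The concern.** Safety information is to be gathered over six months in children taking a daily product, and nothing in the plan commits anyone to report it by arm. The one categorical display looks in one direction only: a child whose digestion deteriorates and a child whose digestion stays the same both count as not improved.

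At stake is the balance of the report. Followed as written, the plan produces benefit percentages for each arm with no counterpart for harm. Two arms could show the same percentage improved while more children on one of them got worse. Events outside the questionnaire outcomes need not appear in any table. A reader of the results could not tell a trial in which few harms occurred from one in which harms were not tabulated.

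**Working it through.** The documents give no adverse event rate, alpha, power or effect size, so there is no stated figure to reproduce. The check has three parts. All rates below are assumptions, and a two-sided alpha of 0.05 is assumed throughout. The arm size of 30 comes from Section 5.4.

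**1. Tracing adverse events through the plan**

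| Place | Content on adverse events |
|---|---|
| 1.3 Schedule | Reviewed at screening, intervention, conclusion |
| 3 Objectives and endpoints | None |
| 6.4 Withdrawal | Ground for withdrawing an individual child |
| 7 Statistical considerations | None: no analysis set, no summary by arm |

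**2. What each planned summary would show if harm falls on a subset**

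Assumed digestion results with 30 children per arm:

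| | Improved | Unchanged | Worse |
|---|---|---|---|
| Product | 15 | 6 | 9 |
| Placebo | 15 | 13 | 2 |

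- Percentage improved (planned): 15/30 = 50% in both arms, so no difference.
- Between-arm test (planned; score +1, 0, −1): mean change is (15 − 9)/30 = 0.20 on product and (15 − 2)/30 = 0.43 on placebo. The direction is unfavourable to the product, but the t-test gives p = 0.24 and the Mann-Whitney test p = 0.40.
- Percentage worsened (not planned): 9/30 = 30% versus 2/30 = 7%, a difference of 23 percentage points (Newcombe 95% CI about 4 to 42), Fisher exact p = 0.042.

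Sensitivity of that last p-value to the assumed counts:

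| Worse, product vs placebo | Fisher p |
|---|---|
| 10 vs 2 | 0.021 |
| 9 vs 2 | 0.042 |
| 8 vs 2 | 0.080 |
| 9 vs 3 | 0.10 |

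Moving one child takes the result across 0.05, so the p-value itself carries little weight. The contrast between the three summaries does not depend on it. In a second assumed table (12 improved in each arm, 10 versus 2 worse), percentage improved is 40% in both arms and the change-score tests give p = 0.17 (t) and 0.26 (Mann-Whitney), against p = 0.021 for worsening.

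**3. What an adverse event table could show at 30 per arm**

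Chance of seeing at least one event in an arm, 1 − (1 − p)^30:

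| True rate p | Chance |
|---|---|
| 1% | 26% |
| 2% | 45% |
| 5% | 79% |
| 10% | 96% |

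If no event of a type is seen in 30 children, the one-sided 95% upper limit is 1 − 0.05^(1/30) = 9.5%, and the two-sided exact limit is 1 − 0.025^(1/30) = 11.6%.

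Power to separate two rates, with p̄ their mean: Φ{(|p1 − p2| − 1.96·√[2p̄(1 − p̄)/30]) / √[(p1(1 − p1) + p2(1 − p2))/30]}.

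| Placebo vs product | Power |
|---|---|
| 5% vs 20% | 0.42 |
| 5% vs 30% | 0.73 |
| 10% vs 30% | 0.49 |
| 10% vs 40% | 0.78 |

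Worked for 10% vs 30%: (0.20 − 1.96 × 0.1033)/0.1000 = −0.024, and Φ(−0.024) = 0.49.

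Only large differences would be detected with good power, so such a table is descriptive.

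**The case against.** A reader might infer that harm, digestive worsening included, is never compared between the arms. The documents do not support that. Section 7 plans between-arm tests of health outcomes against placebo and does not limit their direction. Digestion, illness count and weight are all secondary outcomes. The improvement percentages are an addition to those tests, not a replacement. In the example above, the planned test does point the unfavourable way. Unstated sidedness and endpoints worded as gains are under-specification, not an absent comparison. This objection stands, and it limits the point to adverse events and to worsening in a subset.

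A reader might also infer that the dairy content makes digestive harm on the product likely. The product contains whey and milk protein concentrate and the listed placebo ingredients do not. However, Section 5.2 excludes children with dairy allergy or lactose intolerance, and children in either arm may mix the powder with milk. The ingredient difference is real, but it does not establish expected harm, and the point does not need it.

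Nor do the documents show that the trial exists to support marketing. The reference to marketing claims in Section 4.3 is part of the reason for using the commercial dosage, next to a second reason about understanding the formulation. The objectives are those in Section 3.

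Two further cautions stand. The 9.5% limit follows from having 30 children, and no reporting change alters it. The questionnaires are not in the documents, so it cannot be confirmed that every digestion item can register worsening, or that the adverse event record supports every proposed category.

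None of this supplies what is missing: no part of the documents plans an adverse event summary by arm or a percentage worsened.

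**Conclusion.** The point holds in this form: adverse events are reviewed in every phase, no objective, endpoint or analysis summarises them by arm, and the only categorical summary merges worsened with unchanged children. Mean worsening in digestion falls within a planned comparison, but that comparison is weak against harm in a subset and does not reach adverse events.

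The size can only be illustrated. With assumed worsening of 30% versus 7% and equal improvement, the planned percentages show no difference and the planned between-arm test gives p = 0.24 or 0.40, depending on the test chosen. The finding about adverse events rests on the text alone and needs no assumed rate. This should be corrected. It does not undermine the primary cognitive comparison.

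**What to change.** - **Section 3:** add safety and tolerability as a secondary objective.
- **Section 7, adverse events:** for all children who took any product, tabulate by arm the number and percentage with any adverse event, with digestive events, and with events leading to discontinuation. Give a 95% confidence interval for each between-arm difference, and label the table descriptive at 30 per arm.
- **Section 7, percentages:** report the percentage worsened beside the percentage improved for every item whose response scale allows it, with unchanged children shown separately from both.
- **Section 7, tests:** state that between-arm tests are two-sided.

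The cost is a few sentences and two more tables. No extra visits, measurements or participants should be needed, provided the adverse event record and the questionnaire scales hold the detail required; that should be checked before the text is finalised. The downside for the sponsor is that worsening will be shown next to improvement.

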8 CONSENT, PRIVACY AND OTHER POLICIES

8.1 CONSENT/ASSENT AND OTHER INFORMATIONAL DOCUMENTS PROVIDED TO PARTICIPANTS

Consent forms describing in detail the study intervention, study procedures, and risks are given to the participant, and written documentation of informed consent is required prior to starting intervention/administering study intervention. The following consent materials are submitted with this protocol: an informed consent form and a patient bill of rights.

8.2 Consent Procedures and Documentation

Informed consent is a process that is initiated prior to the individual's agreeing to participate in the study and continues throughout the individual's study participation. Consent forms will be Institutional Review Board (IRB)-approved, and the participant will be asked to read and review the document. These documents will explain the research study to the participant and answer any questions that may arise. A verbal or written explanation will be provided in terms suited to the participant's comprehension of the purposes, procedures, and potential risks of the study and of their rights as research participants. Participants will have the opportunity to carefully review the written consent form and ask questions prior to signing. The participants should have the opportunity to discuss the study with their family or surrogates or think about it prior to agreeing to participate. The participant will sign the informed consent document prior to any procedures being done specifically for the study. Participants must be informed that participation is voluntary and that they may withdraw from the study at any time without prejudice. A copy of the informed consent document will be given to the participants for their records. The informed consent process will be conducted and documented in the source document (including the date), and the form will be signed before the participant undergoes any study-specific procedures. The rights and welfare of the participants will be protected by emphasizing to them that the quality of their medical care will not be adversely affected if they decline to participate in this study.

8.3 CONFIDENTIALITY AND PRIVACY

Participant confidentiality and privacy is strictly held in trust by the participating investigators, their staff, and the sponsor(s) and their interventions. This confidentiality is extended to cover testing of biological samples and genetic tests in addition to the clinical information relating to participants (not applicable to this study). Therefore, the study protocol, documentation, data, and all other

information generated will be held in strict confidence. No information concerning the study or the data will be released to any third party without prior written approval of the sponsor.

The study participant's contact information and records will be securely stored on an AWS server. At the end of the study, all records will continue to be kept in a secure location for as long a period as dictated by the reviewing IRB, Institutional policies, or sponsor requirements.

8.4 DATA COLLECTION AND MANAGEMENT RESPONSIBILITIES

Data collection is the responsibility of Citruslabs, which is responsible for ensuring the accuracy, completeness, legibility, and timeliness of the data reported.

Trial data will be entered into a 21 CFR Part 11-compliant data capture system provided by Citruslabs. The data system includes password protection and internal quality checks, such as automatic range checks, to identify data that appear inconsistent, incomplete, or inaccurate. Clinical data will be entered directly from the source documents.

8.5 PROTOCOL DEVIATIONS

A protocol deviation is any noncompliance with the clinical trial protocol, International Conference on Harmonisation Good Clinical Practice (ICH GCP), or Manual of Procedures (MOP) requirements. The noncompliance may be either on the part of the participant, the investigator, or the CRO staff. As a result of deviations, corrective actions are to be developed by the trial administrator (Citruslabs) and implemented promptly.

It is the responsibility of Citruslabs to use continuous vigilance to identify and report deviations within 7 working days of identification of the protocol deviation or within 7 working days of the scheduled protocol-required activity. Protocol deviations must be sent to the reviewing Institutional Review Board (IRB) per their policies. Citruslabs is responsible for knowing and adhering to the reviewing IRB requirements.

8.6 Publication and Data Sharing Policy

This study will be conducted in accordance with the following publication and data sharing policies: the study may be published in an open-access preprint server. The study administrators (Citruslabs) will be acknowledged in any publications relating to this study. This trial may be registered with clinicaltrials.gov, and results may be submitted to clinicaltrials.gov following publication. No part of this study, including protocol and results, may be published in any form without explicit prior approval in writing by the study sponsor.

8.7 CONFLICT OF INTEREST POLICY

The independence of this study from any actual or perceived influence is critical. Therefore, any actual conflict of interest of persons who have a role in the design, conduct, analysis, publication, or any aspect of this trial will be disclosed and managed. Furthermore, persons who have a perceived conflict of interest will be required to have such conflicts managed in a way that is appropriate to their participation in the design and conduct of this trial. Any employees of, or people with any connection to, the sponsor or Citruslabs will not be eligible for participation in this study.

The sponsor has a conflict of interest in that they may benefit financially from the success of the study. To manage the conflict of interest, an independent third party (Citrusabs) will be handling

all design and administration of participant-focused materials, all participant recruitment and data gathering, and data analysis.

